## 9.3.2. Primary Endpoint Analysis

The primary endpoint is the incidence and severity of AEs and AESIs, incidence of SAEs, changes in laboratory test results, vital signs, and ECG results.

AEs will be coded using the latest version of the MedDRA classification system.

All AEs starting on or after the first infusion will be categorized as TEAEs.

TEAEs will be presented by SOC and PT, and will include the percentage of participants reporting at least one TEAE by SOC and PT and overall.

Multiple occurrences of a single PT in a participant will be counted only once at the maximum severity/grade.

The number and percentage of participants with most common AEs will be presented.

AEs with missing severity or relationship to IMP will be classified as severe and treatment-related, respectively. All AEs will be summarized by relatedness to IMP.

Any AEs leading to death or discontinuation of IMP will also be summarized.

All AE data will be listed.

The other safety endpoints will be summarized using descriptive statistics.

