## 8.1. Disposition

The number of participants will be summarized for ENR for the Final Planned Analysis (FPA). The number of participants per country and site will also be provided using the SAF for the FPA. The number of participants who completed or discontinued the treatment using the SAF, for IA and FPA and/or the study along with the reason for discontinuation will be summarized using the FAS for both the IA and FPA.

Participant disposition and withdrawals will be presented for the FAS set. Data will be tabulated at least for;

- participants each analysis sets for the FPA
- number and percentage of participants who roll over from OLE study 2104 for the FAS, IA and FPA.
- number and percentage of participants completed, or discontinued the study for the IA and FPA.
- number and percentage of participants for each study discontinuation reason or the IA and FPA.
- number and percentage of participants discontinuing treatment but continuing study assessments for the IA and FPA.

A listing of participant disposition will be prepared to present information about treatment allocation, treatment discontinuation and study discontinuation.

Document: BIOSdata\argenx\Efgartigimod\HAB40220\Biostatistics\Documentation\SAP

Author: Version Number: 1.0

Version Date: 03 June 2024

Template No.: CS\_TP\_BS016 Revision 7 Reference: CS\_WI\_BS005

Page 26 of 54

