#### 14.1. **Adverse Events**

AEs and SAEs will be collected as defined in the section 10.3 of the protocol. Refer to the criteria in Appendix 1 for which AEs collects in POTS will be added into POTS-OLE. AEs will be coded using latest version of Medical Dictionary for Regulatory Activities (MedDRA) central coding dictionary. AEs will be graded using the National Cancer Institute (NCI) Common Terminology Criteria for Adverse Events (CTCAE) version 5.0. For each AE, start and stop date/times are collected as well as severity, a seriousness flag, treatment-relatedness, relatedness to procedures, action taken towards the study drug and outcome.

Treatment-emergent adverse events (TEAEs) are defined as AEs with onset on or after the first administration of IMP in this 2105 study up to and including 60 days after the last IMP administration before the event (refer to schematic).

D1: IMP start	D40: Start IMP interruption		D120: IMP restart	D160: Start IMP disc			D240: Study disc		
IMP					IMP				
TE: D1-D40	TE: days	D40+60	Non-TE: 119	D101-	TE:D120-D160	TE: days	D160+60	Non-TE: >D220	

AEs will be considered treatment-emergent based on their start date/time. If the AE start date/time is incomplete or missing, the AE will be considered treatment-emergent unless the available part of the AE start or stop date/time

Document: BIOSdata\argenx\Efgartigimod\HAB40220\Biostatistics\Documentation\SAP

1.0 Version Number: Author:

> Version Date: 03 June 2024

Template No.: CS\_TP\_BS016 Revision 7 Reference: CS\_WI\_BS005

Page 30 of 54

provide evidence that the event did not occur within 60 days from last IMP administration before the event.

AE onset and duration will be calculated as follows when start and stop dates are fully known: AE onset day (vs. first administration)

- $\circ$  AE start date  $\geq$  date of first administration: AE start date date of first administration + 1 day
- AE start date < date of first administration: AE start date date of first administration
- AE duration (days) =
- AE end date -AE start date +1 day
- Study discontinuation date =
- AE start date + 1 day (when the AE start date is fully known but the AE is not resolved at the end of the study). In this case the duration will be presented as ">x days".

An AE for which the study drug was discontinued is defined as an AE with action taken "drug withdrawn".

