Severity is classed as mild/moderate/severe/life-threatening/death. If a participant reports a TEAE more than once within that SOC/PT, the AE with the worst-case severity will be used in the corresponding severity summaries.

Relationship, as indicated by the Investigator, is classed as "not related" or "related". If a participant reports the same AE more than once within that SOC/ PT, the AE with the worst-case relationship to IMP will be used in the corresponding relationship summaries.

AEs leading to discontinuation of IMP will be identified by using the "Action taken with Efgartigimod/Placebo due to adverse event" from the AE page of the eCRF.

Adverse event of special interest (AESI) can be serious or nonserious, related, or unrelated to the IMP or study procedures. Infections are considered AESIs and are defined as events with a PT that falls under the MedDRA SOC 'Infections and infestations'.

Infusion/injection related reactions (IRRs) are defined as all AEs with a MedDRA PT that is listed in either:

- MedDRA Hypersensitivity SMQ broad selection
- MedDRA Anaphylactic reaction SMQ broad selection
- MedDRA Extravasation events (injections, infusions, and implants) SMQ broad selection, excluding implants and occurs within 48 hours of an infusion/injection, or within 2 days if the AE start time is not available. In case of partially missing AE start date, the AE will be considered an IRR, unless the available parts of the AE start date provide evidence it did not occur within 48 hours of an infusion/injection.

Any deaths during the study are recorded on the "Deaths Details" page of the eCRF. A death case is defined as an AE with outcome 'fatal'. Fatal events will be presented in a summary table presenting overall TEAEs and a data listing along with primary cause of death.

BIOSdata\argenx\Efgartigimod\HAB40220\Biostatistics\Documentation\SAP Document:

1.0 Author: Version Number:

> Version Date: 03 June 2024

Reference: CS WI BS005

Template No.: CS\_TP\_BS016 Revision 7

Page 31 of 54

Summary tables will only include TEAEs. However, all AEs reported during the study will be listed. Summary tables by SOC and PT will be sorted alphabetically.

An overview table of AEs will be presented to show number and percentage of participants with at least one event, and the number of events and the event rate per 100 PYFU, for the SAF at the IA and FPA for the following;

- TEAEs (IA and FPA)
- Serious TEAEs (IA and FPA)
- Grade ≥3 TEAEs (IA and FPA)

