### 14.2.1. Laboratory Specific Derivations

All datapoints obtained after informed consent up to database cutoff will be considered. The following abnormality categories will be defined:

- Low: value < lower limit of normal range
- Normal: lower limit of normal range  $\leq$  value  $\leq$  upper limit of normal range
- High: value > upper limit of normal range
  - Notes:
  - Classification will be done in standardized units, using non imputed values and limits.
  - For the worst-case analysis visits, as defined in section 6.4, an additional category low + high is defined in case there are both low and high post-baseline values.

Toxicity grades will be computed according to the National Cancer Institute (NCI) common toxicity criteria for adverse events (CTCAE) toxicity grading list (version 5.0). The implementation of these toxicity grades for analysis

BIOSdata\argenx\Efgartigimod\HAB40220\Biostatistics\Documentation\SAP Document:

1.0 Author: Version Number:

> Version Date: 03 June 2024

Template No.: CS\_TP\_BS016 Revision 7 Reference: CS\_WI\_BS005

Page 34 of 54

is presented in appendix 2. Only the parameters described in appendix 2 will be computed, according to the declared limits for each grade.

Only lab parameters specified within the protocol will be analyzed and, only those both in the protocol and in appendix 2 will be considered for toxicity, all others that are in the protocol and not in appendix 2 but have High/Low/Normal will be presented in the abnormality table.

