## 14.4. Vital Signs

The following Vital Signs measurements will be reported for this study for SAF at the IA and FPA.:

- Systolic Blood Pressure (mmHg)
- Diastolic Blood Pressure (mmHg)
- Pulse Rate (bpm)
- Respiratory Rate (breaths/min)
- Oral Temperature (°C)

Vital signs parameters will be summarized using descriptive statistics at each analysis visit. Abnormalities will be presented as cross-tabulations of the abnormality at each post-baseline analysis visit.

All datapoints obtained after informed consent up to 60 days after IMP discontinuation or database cutoff will be considered.

The following summaries will be provided for vital signs data:

Vital signs parameters will be summarized using descriptive statistics at each analysis visit.

Abnormalities will be presented as cross-tabulations of the abnormality at each postbaseline analysis visit and at the worst-case analysis visit versus the baseline abnormality.

All vital signs data will be listed, but only for participants with any postbaseline abnormality.

Document: BIOSdata\argenx\Efgartigimod\HAB40220\Biostatistics\Documentation\SAP

Author: Version Number: 1.0

Version Date: 03 June 2024

Template No.: CS\_TP\_BS016 Revision 7 Reference: CS\_WI\_BS005

Page 36 of 54

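### The SAP closes the treatment-emergent window 60 days after the latest dose where the protocol leaves it open; the change is undeclared and alters the counts for interruptions over 60 days and for follow-up or reports beyond the window

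*SAP*

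**What the plan says.** Protocol 9.3.2 defines treatment-emergence by a start only: "All AEs starting on or after the first infusion will be categorized as TEAEs". Protocol 9.3.1.1 describes outcomes through the end of scheduled follow-up.

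SAP 14.1 keeps the same start but adds an end: "up to and including 60 days after the last IMP administration before the event". The window reopens on re-dosing. A schematic shows a participant who interrupts on D40, restarts on D120, stops drug on D160 and leaves the study on D240. It marks D101-119 and everything after D220 as not treatment-emergent.

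SAP 14.1 then says: "Summary tables will only include TEAEs. However, all AEs reported during the study will be listed". The overview rows for serious, fatal and special-interest events are all treatment-emergent rows. On deaths: "Fatal events will be presented in a summary table presenting overall TEAEs and a data listing along with primary cause of death".

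The visible text under SAP 3.4, the section for changes from the protocol, has only a displaced sentence on baseline.

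The other safety data have different cuts. For laboratory data SAP 14.2.1 says "All datapoints obtained after informed consent up to database cutoff will be considered", and SAP 14.3 says the same for ECG. For vital signs SAP 14.4 says "All datapoints obtained after informed consent up to 60 days after IMP discontinuation or database cutoff", and SAP 14.5 repeats this for physical examination.

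**The concern.** Incidence of adverse events, events of special interest (infections) and serious adverse events is the primary endpoint. Two definitions of which events count, one in each document, can give two answers to the primary question, and a reader of the SAP is not told that the rule changed.

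The difference does not fall evenly. It cannot touch a participant dosed and followed on schedule. It touches those who interrupt for a long time or stay under observation off drug. Protocol 7.1.2 names related serious events and related, clinically significant infections as possible reasons to interrupt, and protocol 8.4.6 allows interruption after an event of special interest. A safety event can therefore start the very period in which later events are not tabulated.

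**Working it through.** **Inputs**

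| Input | Value | Source |
|---|---|---|
| Last treatment-emergent day, SAP | latest dose day L + 60 | SAP 14.1 |
| Last treatment-emergent day, protocol | none | Protocol 9.3.2 |
| End of routine event collection | safety follow-up visit (SFV) | Protocol 8.4.1 |
| SFV timing | L + 56 ± 3, so at most L + 59 | Protocol Table 2 and 7.1.1; SAP 6.3 |
| Last scheduled dose | day 323 (Q2W), day 330 (QW after a switch) | Protocol 4.1 |
| Maximum length of an interruption | not stated | Protocol 7.1.2 |
| Expected participants | about 38 | Protocol 9.5 |

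**1. The SAP's schematic reproduces.** Take D40 and D160 as the last dose days before each gap.
- Interruption: 40 + 60 = D100, so D101 to D119 is excluded: 119 − 100 = 19 days.
- After stopping: 160 + 60 = D220, so D221 to D240 is excluded: 240 − 220 = 20 days.
- Together: 19 + 20 = 39 of 240 days, or 16%. Under the protocol definition the figure is 0.

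**2. Participants followed on schedule lose nothing.**
- Q2W completer: SFV by 323 + 59 = day 382; SAP window ends 323 + 60 = day 383.
- QW completer: SFV by 330 + 59 = day 389; SAP window ends 330 + 60 = day 390.
- Permanent discontinuer under 7.1.1, any L: collection ends by L + 59, window ends at L + 60.

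The margin is one day in each case, so the two definitions give the same count.

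**3. Where the definitions part**

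| Situation | Days excluded by the SAP only | Schematic |
|---|---|---|
| Interruption, restart on day R | R − L − 61, if positive | 120 − 40 − 61 = 19 |
| Off drug, events still collected to day E | E − L − 60, if positive | 240 − 160 − 60 = 20 |
| Late SFV, s days after the last dose | s − 60, if positive | not shown |
| Related serious event notified after the study (8.4.1) | any onset after L + 60 | not shown |

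**4. Effect on the reported figures.** SAP 7.2 uses all participants in the analysis set as the denominator for event percentages. An excluded event leaves the numerator while its participant stays in the denominator. One participant is 1/38 = 2.6 percentage points. The rate per 100 person-years is different: SAP 14.1 restricts its denominator to treatment-emergent time (201 of 240 days in the schematic), so that rate is consistent with its own numerator.

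**5. Chance of an excluded event.** The documents give no event rates. Assume a constant rate r of 0.05 to 1.0 events per person-year. For the schematic's 39 days, 1 − exp(−r × 39/365.25) runs from 0.5% to 10% per participant with such a gap.

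**6. Data cuts side by side.** SAP 6.5 calls any post-baseline abnormality absent at baseline treatment-emergent, with no end date, and laboratory and ECG data run to database cutoff. Take D110 in the schematic. A new laboratory abnormality counts as treatment-emergent. If it is clinically significant, protocol 8.3.4 requires it to be recorded as an adverse event, and that event, with onset on D110, does not count. For vital signs and physical examination the text offers two end points and does not say which governs.

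**The case against.** The best defence is that the window was sized to the follow-up visit. Collection ends at most 59 days after the last dose and the window closes at 60, so a bounded on-treatment definition costs nothing for anyone on schedule. Protocol 9.3.1.1 does not contradict it for them either. Nothing leaves the report: all events are listed, deaths have their own listing with cause, and listings for about 38 participants can be read. Table 2 schedules no chemistry, hematology or ECG at the SFV, so the differing cuts matter little for participants followed under 7.1.1. The schematic illustrates a rule and is not a forecast. The disposition row for "number and percentage of participants discontinuing treatment but continuing study assessments for the IA and FPA" could be filled by someone between stopping drug and the SFV.

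Most of this stands, and it sets the limits of the point. It does not cover interruptions, for which no maximum length is given and during which collection continues. Nor does it settle follow-up off drug: Table 2 footnote b provides for participants who stop drug but remain in the study, while 7.1.1 describes only an early discontinuation visit and an SFV.

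A reader might go further and infer that an early stopper loses most of their follow-up. Stopping on day 57 and staying to day 337 would leave 337 − 117 = 220 days outside the window. The documents do not support this as an expected loss: under 8.4.1 and 7.1.1 routine collection ends by 57 + 59 = day 116, inside a window that closes on day 117.

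**Conclusion.** The definitions conflict, the conflict bears on the primary endpoint, and the visible text of SAP 3.4 does not declare it. The consequence is narrow. It is zero for completers and for discontinuers followed under 7.1.1 with an on-time SFV. It arises for interruptions over 60 days, for participants off drug who remain beyond the SFV window, for a late SFV, and for serious events reported after the study. In those cases adverse events, serious events, infections and deaths would be missing from the summary tables but kept in the listings. It would be wrong to infer that they vanish from the report, or that the person-time rates are mismatched.

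The size cannot be fixed from the documents. The only worked case is the schematic (39 of 240 days), and each participant with an omitted first event moves a percentage by 2.6 points if 38 enrol. This rests on collection ending at the SFV as 8.4.1 states, and on D40 and D160 being last dose days in the schematic. Whether serious events reported after the study reach the analysis database is not stated.

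**What to change.** Preferred: use the protocol 9.3.2 definition for the adverse event, serious event, special-interest and fatal-event tables. Add a row splitting onset at or within 60 days of the latest dose from onset later than that, with person-time matched to each part.

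Alternative: keep the 60-day window, declare and justify it in SAP 3.4, and add one table of all serious events, infections and deaths from the first dose in this study to the end of participation, regardless of the window.

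In either case:
- State one consistent data cut for laboratory data, ECG, vital signs and physical examination, and say which end point governs where the text now offers two.
- Reconcile Table 2 footnote b, protocol 7.1.1 and SAP 8.1 on follow-up after stopping drug, including whether adverse events are collected after the SFV.

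The cost is SAP wording plus one row per overview table, or one extra table. The downside of the preferred option is that a few off-drug events enter the headline count; the split row shows them separately.

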### Events to be Collected as AEs

- Any abnormal laboratory test results (hematology, clinical chemistry, or urinalysis) or other safety assessments (eg, ECG, radiological scans, vital sign measurements), including those that worsen from baseline, considered clinically significant in the medical and scientific judgment of the investigator (ie, not related to progression of underlying disease)
- Exacerbation of a chronic or intermittent pre-existing condition including either an increase in frequency and/or intensity of the condition
- New condition detected or diagnosed after IMP administration even though it could have been present before the start of the study
- Signs, symptoms, or the clinical sequelae of a suspected intervention-intervention interaction
- Signs, symptoms, or the clinical sequelae of a suspected overdose of either IMP or a
  concomitant medication. Overdose per se will not be reported as an AE/SAE unless it is an
  intentional overdose taken with possible suicidal/self-harming intent. Such overdoses will
  be reported regardless of sequelae.
- Lack of efficacy or failure of expected pharmacological action per se will not be reported as an AE or SAE. Such instances will be captured in the efficacy assessments. However, the signs, symptoms, and/or clinical sequelae resulting from lack of efficacy will be reported as AE or SAE if they fulfill the definition of an AE or SAE.

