# Criterias of prior/concomitant medications, Medical history and AEs from POTS to POTS-OLE

POTS Form	Criteria when met in POTS, the respective record will be added into
	POTS-OLE
Adverse Event (Eg. HEADACHE)	Outcome = Recovering/Resolving or Not Recovered/Not Resolved or Unknown     Prior and Concomitant Medications = Ongoing with Indication = Adverse Event (HEADACHE)

Document: BIOSdata\argenx\Efgartigimod\HAB40220\Biostatistics\Documentation\SAP

Author: Version Number: 1.0

Version Date: 03 June 2024

Template No.: CS\_TP\_BS016 Revision 7 Reference: CS\_WI\_BS005

Simple to the second se

Page 51 of 54

Medical History (Eg. HEADACHE)	Ongoing     Prior and Concomitant Medications = Ongoing with Indication = Medical History (HEADACHE)
Related Procedures/Surgeries (Eg. Cataract extraction)	Ongoing     Prior and Concomitant Medications = Ongoing with Indication = Related Procedures/Surgeries (Cataract extraction)
Prior and Concomitant Medications	Ongoing

Document: BIOSdata\argenx\Efgartigimod\HAB40220\Biostatistics\Documentation\SAP

Author: Version Number: 1.0

Version Date: 03 June 2024

Template No.: CS\_TP\_BS016 Revision 7 Reference: CS\_WI\_BS005

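### SAP 14.1 sets TEAE status by start date alone, so adverse events carried over from study 2104 can be misclassified when they worsen or when their start date is incomplete

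*SAP*

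**What the plan says.** SAP 14.1 gives the definition: "Treatment-emergent adverse events (TEAEs) are defined as AEs with onset on or after the first administration of IMP in this 2105 study". The window closes 60 days after the most recent dose preceding the event. Status depends on one attribute: "AEs will be considered treatment-emergent based on their start date/time". Protocol 9.3.2 also defines TEAEs by start relative to the first infusion. Neither text mentions an event that was present before dosing and then worsened.

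SAP 14.1 refers to Appendix 1 for the parent-study events that are added to the extension data. The criterion there is "Outcome = Recovering/Resolving or Not Recovered/Not Resolved or Unknown".

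For tabulation, SAP 14.1 says "Summary tables will only include TEAEs", with all other events listed. The overview rows for serious, Grade ≥3, fatal, special-interest and IMP-discontinuation events are all TEAE rows.

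For incomplete dates the default is: "If the AE start date/time is incomplete or missing, the AE will be considered treatment-emergent". The only way out is when what is known of the onset or end date shows that the event fell outside the 60-day window. No exception is made for carried-over records.

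Three other places bear on this:
- Protocol 10.3.1 collects as an AE "Exacerbation of a chronic or intermittent pre-existing condition including either an increase in frequency and/or intensity of the condition".
- Protocol 9.3.2 promises a summary of AEs leading to death or IMP discontinuation, without limiting it to TEAEs.
- SAP section 10 presents events up to 2104 week 24 as medical history, and those still ongoing as concomitant illnesses.

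**The concern.** The primary endpoint includes the incidence and severity of AEs and AESIs and the incidence of SAEs. Carried-over events are a known class of record in this study, and the date rule can misplace them in two ways.

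First, severity, seriousness and outcome are collected as attributes of each AE, and SAP 14.1 defines a death case as an AE with a fatal outcome. A change in any of them can therefore be entered on a record that keeps its 2104 start date. The tables then omit a deterioration that happened on extension treatment. This matters most for former placebo participants, whose first efgartigimod dose is on extension day 1, and for infections, which are the AESI.

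Second, a record known to come from 2104 can be tabulated as new in 2105 only because part of its start date is missing.

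**Working it through.** **1. Reproduce the SAP's schematic.** Rule: TEAE if onset day ≥ 1 and onset day minus the last IMP day before onset ≤ 60. With dosing on D1–D40 and D120–D160, status is TEAE from D1, non-TEAE from D101 (40 + 60 = 100 is the last included day), TEAE from D120 and non-TEAE from D221 (160 + 60 = 220). This matches the SAP.

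**2. Carried-over event, complete start date.** Take the 168 possible onset days in the 24 weeks (24 × 7) before the first 2105 dose. All are before day 1, so the event is a TEAE for 0 of 168, whatever its later grade, seriousness or outcome.

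**3. The same event after it worsens in 2105, under each way of recording it.**

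| How the worsening is recorded | Start date used | Status | SAP AE summary tables | Listings |
|---|---|---|---|---|
| Existing record updated | in 2104 | non-TEAE | absent | present |
| New AE under protocol 10.3.1 | in 2105 | TEAE, if within 60 days of the last dose | present | present |

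Protocol 10.3.1 says an exacerbation is collected. It does not say that an AE already open gets a second record and a new start date. Protocol 8.4.3 has SAEs and AESIs followed to resolution or stabilisation, which is compatible with updating in place. Protocol 10.1.8 leaves data-entry guidance to an eCRF completion document that is not among the documents reviewed.

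**4. Carried-over event, incomplete start date.** The rule was applied as TEAE unless the known parts exclude the window from the first 2105 dose to the last dose + 60 days. Stop-date evidence was assumed absent, as is likely for unresolved events. Assumed first doses are in May 2024, to show a range.

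| First 2105 dose | Day missing | Day and month missing | Whole date missing |
|---|---|---|---|
| 1 May | 0/168 | 121/168 | 168/168 |
| 10 May | 9/168 | 130/168 | 168/168 |
| 15 May | 14/168 | 135/168 | 168/168 |
| 28 May | 27/168 | 148/168 | 168/168 |

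The first column is the day of the month minus 1, because a start month before the dosing month excludes the event. The second is the days elapsed in the year: 31 + 29 + 31 + 30 = 121, plus 0, 9, 14 or 27. It depends on the assumed date and would be 0 for a first dose on 1 January. If a carried-over record counted as evidence of earlier onset, every cell would be 0.

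**5. Weight of one participant.** The planned size is about 38: 1/38 = 2.6 points. With 2:1 randomisation in 2104 and equal roll-over, former placebo participants number 38/3 ≈ 13: 1/13 ≈ 7.7 points. Protocol 9.3.1 calls for summaries by parent treatment.

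**The case against.** A reader might infer that every carried-over event that worsens is bound to drop out of every summary table. The documents do not support that. Protocol 10.3.1 can reasonably be read as making an exacerbation a new AE with onset in 2105, and the eCRF completion document may already say so. Protocol 9.3.2 promises a summary of AEs leading to death or IMP discontinuation with no TEAE limit. The laboratory, vital-sign and ECG tables compare with baseline (SAP 6.5), so only AE tables are affected.

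Nor would the signal be lost. All AEs are listed, deaths have their own eCRF page and a listing, and SAEs and AESIs are reported within 24 hours. In about 38 participants the listings can be read in full. Clinically significant active infection is also screened at entry (protocol 2.3.1 and 5.2), which limits the infection example.

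On incomplete dates, defaulting to TEAE is the usual conservative choice, a missing day alone seldom matters, and SAP section 10 already treats events up to 2104 week 24 as medical history. A reader might also infer double counting across the two studies, but that depends on the 2104 analysis plan, which is not available.

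These points narrow the concern without removing it. The tables still depend on an unstated recording convention. The SAP's TEAE-only rows are narrower than protocol 9.3.2. SAP section 10 does not override the date default in 14.1. SAP 6.2 lets eCRF information override status only for events starting on the reference date. Appendix 3 names adverse events in its title but assigns only prior or concomitant status.

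**Conclusion.** The concern holds in conditional form. If the existing record is updated, a carried-over event that worsens, becomes serious or becomes fatal in 2105 is left out of the SAP's AE summary tables. If a new record is made, it is included. The documents do not settle which applies. Separately, a carried-over event with an incomplete start date can be tabulated as new, mainly when the month or the whole date is missing.

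Each affected participant moves an incidence by 2.6 points overall, or by about 7.7 points among former placebo participants if roll-over was equal between arms. The number of affected events cannot be estimated from the documents. The study is descriptive, so no test is affected. The issue is whether the primary safety tables are correct and reproducible, and it should be settled before the database lock they depend on.

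**What to change.** 1. In SAP 14.1, also count as a TEAE any AE carried over from 2104 whose grade increases, or which becomes serious or fatal, on or after the first 2105 dose and within the 60-day TEAE window. Date it at the worsening. Count each worsening once, whether it was recorded as an update or as a new record, because the tables also report numbers of events and rates per 100 person-years of follow-up.
2. Class every other AE record carried over under Appendix 1 as non-TEAE, however complete its start date, with a cross-reference to SAP section 10.
3. Reconcile the fatal and IMP-discontinuation tables with protocol 9.3.2, either by removing the TEAE limit there or by listing the departure in SAP 3.4.
4. Confirm that the eCRF completion guidance captures the date of worsening. SAP 14.1 mentions only start and stop dates for each AE.

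The cost is a few SAP lines and one derivation flag. No new assessments are needed. If the eCRF does not yet hold the date of worsening, a line of guidance and site queries on the affected records would be added.
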